7.4 Analysis of Primary Effectiveness Outcome Measure

A mixed effects model will be used to compare the rates of patient engagement in formal addiction treatment for OUD on the 30th day post study enrollment between the baseline and IF evaluation periods. The model for the primary effectiveness will be used to compare the rates of engagement in formal addiction treatment for OUD on the 30th day post-index ED visit between the IFEP and BEP is:

$$\text{logit}(p_{si}) = \alpha + \beta t_{si} + \gamma f_{si} + r_s$$

where

- p_{si} is the probability of success of patient participant i at site s ,
- t_{si} is the calendar time of enrollment of patient participant i at site s ,
- f_{si} is the indicator of whether patient participant i at site s is in the BEP ($f_{si}=0$) or IFEP ($f_{si}=1$), and
- r_s is the random effect of site s , where $r_s \sim N(0, \sigma^2)$.

Note that calendar time is measured in days and defined in Section 3.3.6. In this model, γ captures the effect of implementation facilitation. The model will test a one-tailed hypothesis at the 0.05 level. The null and alternative hypotheses are:

$$H_0: \gamma \leq 0$$

$$H_a: \gamma > 0.$$

Similar to the implementation primary outcome, the main focus is the estimated Risk Difference (RD) defined as the difference between IF and Baseline engagement in treatment success rates, ($p_{IFEP} - p_{EP}$) with its 95% credible interval (CI). The estimated RD and its 95% CI will be obtained from the Bayesian approach as described in Section 7.3 for the primary effectiveness outcome. The SAS code will be analogous except p1 is now the proportion of patient participants engaged in formal addiction treatment for OUD on Study Day 30 during the BEP and p2 is the now the proportion during the IFEP.

The primary effectiveness outcome will be summarized by site and evaluation period with frequencies and percentages. Results of the Bayesian approach, that is the model specified above, will be presented tabularly with estimates and 95% credible intervals for the risk difference.

7.5 Supportive Analyses of the Primary Outcome Measures

7.5.1 Subgroup Analyses

The NIH requires subgroup analyses by sex, race, and ethnicity (NIH, 2016). Analyses will be conducted by evaluation period. Primary implementation and effectiveness outcomes will also be summarized by these subgroups and evaluation period.

Several covariates may influence the primary implementation and effectiveness outcome measures. The GLMM models proposed for the primary outcomes will be expanded to adjust for potential effect modifiers. The models will be adjusted for sex, race, and ethnicity as well as each of their interactions with treatment. Below is a mathematical formulation of the models:

$$\begin{aligned} \text{logit}(p_{si}) = & \alpha + \beta t_{si} + \gamma f_{si} + \theta_1 \text{sex}_{si} + \theta_2 \text{race}_{si} + \theta_3 \text{ethnicity}_{si} \\ & + \theta_4 f_{si} * \text{sex}_{si} + \theta_5 f_{si} * \text{race}_{si} + \theta_6 f_{si} * \text{ethnicity}_{si} + r_s \end{aligned}$$

where sex, race, and ethnicity are indicators for their respective variables. They will be entered into the model in a stepwise manner using a p-value cutoff of 0.05. Note that an interaction term will always be included with its corresponding main effects, and the effect of treatment period will be forced into the model. If there are convergence issues, the model will be fit with each demographic factor separately. A forest plot will summarize the estimated risk difference from models where each demographic factor is considered separately to evaluate potential in trends in effect modification, which may not be statistically significant at the 0.05 level.

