IFEP	N	X.x	X.xx; X.xx
Sex			
Male	N	[ref]	[ref]
Female	N		
Race			
White	N	[ref]	[ref]
Black/African American	N		
Other	N		
Ethnicity			
Not Hispanic/Latino	N	[ref]	[ref]
Hispanic/Latino	N		
Sex-by-study phase interaction ²			
Male	N	X.x	X.xx; X.xx
Female	N	X.x	X.xx; X.xx
Race-by-study phase interaction ²			
White	N	X.x	X.xx; X.xx
Black	N	X.x	X.xx; X.xx
Other	N	X.x	X.xx; X.xx
Ethnicity-by-study phase interaction ²			
Not Hispanic/Latino	N	X.x	X.xx; X.xx
Hispanic/Latino	N	X.x	X.xx; X.xx

¹ Note that only covariates which remained in the final covariate-adjusted model will be included in this table.

² Coefficient and corresponding credible intervals are presented for the intervention effect in a particular subgroup (e.g., males).

Table 20: Summary of MOUD Practices by Site Over Time from EHR-abstracted Data

	Baseline Evaluation Period					IF Evaluation Period				
	MA Johns Hopkins ED	GNY Mount Sinai ED	OV University of Cincinnati ED	PNW Harborview Medical Center ED	Total	MA Johns Hopkins ED	GNY Mount Sinai ED	OV University of Cincinnati ED	PNW Harborview Medical Center ED	Total
Buprenorphine										
Administered	N									
Prescribed	N									
Administered and prescribed	N									
Unique providers administering or prescribing	N									
Naloxone										
Dispensed	N									
Prescribed	N									
Dispensed and prescribed	N									
Unique providers dispensing or prescribing	N									
X-waiver										
Physicians	N									
APPs	N									
Additional staff (counselors/peers)	N									

Table 21: COVID-19 Sensitivity Analyses Results for Primary Implementation Outcome

Sensitivity Analysis	GLMM		Bayesian Analysis		
	Intervention Coefficient	p-value	Risk Difference Estimation Time Point	Risk Difference	95% Credible Interval
Pre-COVID data	X.xx	x.xxx	Mid-point (day 632)	X.xx	X.xx; X.xx
			COVID-19 Pause (day 1423)	X.xx	X.xx; X.xx
COVID pause removed	X.xx	x.xxx	Mid-point (day 632)	X.xx	X.xx; X.xx
			COVID-19 Pause (day 1423)	X.xx	X.xx; X.xx

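### Tables 19 and 28 print only demographic terms that survive stepwise selection at p<0.05, so null-to-moderate subgroup differences shown there are exaggerated and their 95% intervals under-cover

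*SAP*

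**What the plan says.** SAP 7.5.1 describes subgroup analyses by sex, race and ethnicity as an NIH requirement. It first states: "The models will be adjusted for sex, race, and ethnicity as well as each of their interactions with treatment". It then makes inclusion conditional: "They will be entered into the model in a stepwise manner using a p-value cutoff of 0.05". Two constraints apply: "an interaction term will always be included with its corresponding main effects", and the period effect is forced in. Protocol 12.14.2 has the same stepwise rule.

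Footnote 1 to Table 19 (implementation outcome) says "only covariates which remained in the final covariate-adjusted model will be included in this table", and Table 28 (effectiveness outcome) carries the same footnote. Footnote 2 to each table explains that the interaction rows give the period effect within each subgroup, with a 95% credible interval. Neither table has a p-value column, and no adjustment for selection is described.

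Two other outputs do not depend on selection. SAP 7.5.1 says "Primary implementation and effectiveness outcomes will also be summarized by these subgroups and evaluation period"; these are Tables 16–18 and 25–27. It also says "A forest plot will summarize the estimated risk difference from models where each demographic factor is considered separately".

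**The concern.** An estimate printed only when it passes a significance threshold is, on average, further from zero than the quantity it estimates. An ordinary 95% interval around it does not allow for that. In Tables 19 and 28 a reader would see a demographic subgroup with an apparently different response to implementation facilitation, and nothing on the page would show that the row is there because it passed p<0.05. If nothing passes, the tables hold no model-based subgroup result for an analysis that the SAP calls required. The two opening statements of 7.5.1 also conflict, since a model cannot both adjust for all three factors and omit those that miss the cutoff.

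**Working it through.** **The plan's own figure.** The documents give no power, error-rate or precision figure for the subgroup models. Their only power statement (SAP 10.2) is that the primary test exceeds 0.8 in two scenarios at ICC below 0.3 and is lower in the other two. Simulating the stated design (4 sites, 120 + 120 patients each, 3-month offsets, linear month, one-sided 0.05, site as a fixed effect, ICC 0) gives 0.97 for 5% to 25% and 0.89 for 25% to 50%. It gives 0.42 for 15% to 25% and 0.56 for 25% to 40%. The stated pattern is reproduced.

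**Inputs.** From the documents: 960 patients, so 480 per period; implementation rates of 15% (the upper planning value) and 25%; cutoff 0.05. Assumed: 30% women, so 336 men and 144 women per period; a two-sided Wald test of each interaction; no site or time terms; variances evaluated at 15% and 25% in both sexes.

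**Standard errors on the log-odds scale.**
- Men: variance = 1/(336 × 0.1275) + 1/(336 × 0.1875) = 0.0392
- Women: variance = 1/(144 × 0.1275) + 1/(144 × 0.1875) = 0.0915
- Interaction: SE = √(0.0392 + 0.0915) = 0.362

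**Selected interaction.** For true log ratio δ, let a = 1.96 − δ/SE and b = −1.96 − δ/SE. The probability of selection is P = 1 − Φ(a) + Φ(b), and the mean selected estimate is δ + SE × [φ(a) − φ(b)]/P. At a true ratio of 1.5, δ = 0.405, a = 0.84 and b = −3.08. Then P = 0.20, and the mean is 0.405 + 0.362 × 0.277/0.202 = 0.90, which is 2.2 times the truth.

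**What the tables print.** Of the excess 0.90 − 0.405 = 0.497, women's estimates take the share 0.0915/0.1307 = 0.70 upward and men's take 0.30 downward. With the men's true log odds ratio at log(1.89) = 0.636:
- Women: (1.041 + 0.70 × 0.497)/1.041 = 1.33 times the truth
- Men: (0.636 − 0.30 × 0.497)/0.636 = 0.77 times the truth

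Four million normal draws, restricted to selected trials, give:

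| True ratio | Women, × truth (log) | Men, × truth (log) | Coverage, women | Coverage, men |
|---|---|---|---|---|
| 1 | 1.00 | 1.00 | 0.51 | 0.79 |
| 1.25 | 1.46 | 0.73 | 0.74 | 0.86 |
| 1.5 | 1.33 | 0.77 | 0.87 | 0.91 |
| 2 | 1.16 | 0.86 | 0.95 | 0.95 |
| 3 | 1.04 | 0.96 | 0.97 | 0.96 |

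At a ratio of 1.25 the selected log interaction averages 3.5 times the truth (3.9 times if sign is ignored).

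**Patient-level check.** Logistic models with fixed site, period, factor and interaction were fitted to 4,000 simulated trials per scenario. At 25% to 40%, the size of the selected log interaction is 3.4, 2.0, 1.3 and 1.05 times the truth at ratios 1.25, 1.5, 2 and 3. Coverage of the women's effect is 0.78, 0.90, 0.96 and 0.96. At 5% to 25% and ratio 1.5 the multiple is 3.6. With 45% women, 25% to 40% and ratio 1.5 it is 1.8. Without selection, coverage is 0.946–0.963 for the interaction and 0.946–0.968 for the women's effect.

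**False interactions.** With three independent tests, 1 − 0.95³ = 14.3% of trials per outcome would select at least one. The simulated values are 9.4% (5% to 25%), 13.7% (25% to 40%) and 14.0% (25% to 50%), assuming race split 50/35/15 and 20% Hispanic.

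**The case against.** The strongest reply is that these are supportive analyses and the plan already reports subgroups without selection. That is largely right. Tables 16–18 and 25–27 cover every level of each factor, and the forest plot is meant for trends that miss significance. Period is forced into the model, and the primary test is separate. SAP section 9 treats secondary findings as hypothesis-generating and sets a bar well below 0.05.

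Three limits remain. The descriptive tables are counts and percentages, with no model estimate or interval. The forest plot is absent from the output list in SAP 15.0, whose only figures are 1A, 1B, 2 and 3. The section 9 caution works through p-values, which Tables 19 and 28 do not show.

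A reader might infer that every reported subgroup effect is exaggerated by the interaction multiples and that the intervals are invalid throughout. The documents do not support that. The tables print subgroup-specific effects, which are distorted less than the interaction: here one sex is inflated and the other attenuated, and neither mean is biased when there is no interaction. Zero coverage of a falsely selected interaction is true by construction and only restates the 5% error rate.

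**Conclusion.** The point stands, limited to Tables 19 and 28 and to interactions that are absent or moderate (ratio up to about 1.5, somewhat higher for a low-rate outcome). There the printed subgroup contrast is too large and the intervals usually under-cover. With strong interactions coverage is close to or above nominal, although at a ratio of 2 the log interaction is still about 1.4 times the truth. It would be wrong to conclude that the primary result is affected or that all subgroup reporting is incomplete.

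The sizes rest on assumptions the documents do not supply: the sex, race and ethnicity mix, the true interaction, and interactions screened one at a time with a two-sided test. The SAP states neither the sidedness nor whether main effects are screened first. Wald intervals stand in for credible intervals under diffuse priors. This is a worthwhile reporting improvement with no bearing on the trial's main conclusion.

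**What to change.** - Delete the stepwise rule from SAP 7.5.1 and record this as a change from protocol 12.14.2.
- In Tables 19 and 28, report all three single-factor models in full whatever the p-value. Each contains the factor, period and their interaction, with the same site and time terms as the final primary model. Replace footnote 1 and label the results exploratory.
- State the site and time terms explicitly. The Revised SAP moves the primary model to fixed site without time but does not say whether the subgroup models follow.
- Draw the forest plot from the same models and add it to SAP 15.0.

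This is a free improvement. It needs no new data, and 7.5.1 already plans single-factor models for the forest plot; only their site and time terms need to be aligned.

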7.5.2 Sensitivity Analyses

To account for the pause in enrollment due to the COVID-19 pandemic, two separate sensitivity analyses will be conducted on the primary implementation and primary effectiveness outcomes.

First, the date sites closed enrollment due to the pandemic will be considered as the date closed for the study, whereby the analysis will be performed using only pre-COVID-19 data. This will show the “true” effect of the Implementation Facilitation on EDs with no effect of coronavirus. Secondly, the data entered after sites reopened their ED will be converted so that the pause in enrollment is removed. This will show whether the 3-month delay in recruitment due to COVID-19 had an impact on the primary implementation and primary effectiveness outcome analyses.

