3.3.4 Study Day

Study Day is defined as the number of days post-index ED Visit with Study Day 0 defined as the date eligibility confirmed which is collected on the enrollment forms for segments B and C (i.e., EC0069B, EC0069C).

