3.3.6 Calendar Time

Calendar time for analysis is defined as the number of days since the site opened for enrollment in the baseline evaluation period. Below are the start and end dates for each site in each evaluation period. The start date is defined as the date the site was given access to the eClinical system to begin enrolling participants in the study for that particular evaluation period. The end date is defined as the last day the site was able to enroll participants in the EDC system for each evaluation period. Note that during the IFEP, enrollment was paused due to the COVID-19 public health measures put into place at two sites, Harborview Medical Center and University of Cincinnati. The days enrollment was paused will be considered as part of the primary analysis and several sensitivity analyses will be performed to account for this pause.

Site	Baseline Evaluation Period		IF Evaluation Period			
	Start Date	End Date	Start Date	Date Paused for COVID-19	Date Reopened for COVID-19	End Date
MA Johns Hopkins ED	4/10/2017	4/9/2018	10/9/2018	N/A	N/A	10/8/2019
NY Mount Sinai ED/Beth Israel	7/6/2017	7/5/2018	1/4/2019	N/A	N/A	1/5/2020
OV University of Cincinnati ED	10/9/2017	10/8/2018	4/8/2019	03/13/2020	6/10/2020	7/6/2020
PNW Harborview Medical Center ED	1/2/2018	1/1/2019	7/2/2019	03/3/2020	6/6/2020	10/4/2020

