7.3 Definition of Primary Effectiveness Outcome Measure

The primary effectiveness outcome is patient participant engagement in formal addiction treatment for OUD on the 30th day post-index ED visit. Engagement in formal addiction treatment for OUD is defined as enrollment and receiving formal addiction treatment for OUD on Study Day 30, assessed by patient self-report and confirmed by direct contact with the treating facility and/or treating. Formal addiction treatment for OUD will be those treatments consistent with the American Society of Addiction Medicine's levels of care (1-4) and will include a range of clinical settings including office-based providers of BUP or naltrexone, OTPs, intensive outpatient, inpatient, or residential treatments. Patients do not need to be receiving MAT on the Study Day 30 to be considered engaged in formal addiction treatment for OUD. Participation in a self-help program, such as Narcotics Anonymous, alone will not be considered as engagement in formal addiction treatment for OUD.

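### The pre-COVID sensitivity analysis cuts at the enrolment pause, so for Day-30 engagement it keeps participants at two sites whose outcome falls on or after the pause

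*SAP*

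**What the plan says.** SAP 7.5.2 announces that "two separate sensitivity analyses will be conducted on the primary implementation and primary effectiveness outcomes". The cut-off for the first of these is set as follows: "the date sites closed enrollment due to the pandemic will be considered as the date closed for the study". The section describes the data that remain in these terms: "whereby the analysis will be performed using only pre-COVID-19 data". The SAP then interprets the result as the true effect of Implementation Facilitation "on EDs with no effect of coronavirus". The same cut serves both outcomes, and nothing is said about when the outcome itself falls.

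SAP 3.3.6 records that "enrollment was paused due to the COVID-19 public health measures put into place at two sites" and gives the dates: 13 March 2020 at University of Cincinnati and 3 March 2020 at Harborview, both during the IF evaluation period.

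The two outcomes are timed differently. The implementation outcome is scored from the index ED visit record (SAP 7.1, 7.5.3). The effectiveness outcome is "engagement in formal addiction treatment for OUD on the 30th day post-index ED visit", made operational as "enrollment and receiving formal addiction treatment for OUD on Study Day 30". SAP 3.3.4 fixes the clock, with "Study Day 0 defined as the date eligibility confirmed which is collected on the enrollment forms".

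**The concern.** An enrolment cut-off isolates pre-pandemic data only when the outcome is settled at enrolment. Engagement is settled 30 days later. A participant enrolled in the last month before the pause therefore enters the pre-COVID analysis with an outcome dated on or after the SAP's own pandemic marker.

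The affected participants all sit on one side of the comparison, in the IF period, and at two of the four sites. A change in treatment access, or in the ability to confirm treatment, would therefore not cancel between periods. Ascertainment is exposed as well. Engagement needs a patient report and facility confirmation (SAP 7.3), follow-up attempts continue beyond day 44 (SAP 7.5.4), and missing outcomes count as failures (SAP 7.5.3). At stake is whether the pre-COVID row of SAP Table 29 is what its label and stated interpretation say it is.

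**Working it through.** **Check on the dates.** SAP 7.5.2 calls the pause a 3-month delay. From the 3.3.6 dates, 13 March to 10 June 2020 is 89 days (Cincinnati) and 3 March to 6 June 2020 is 95 days (Harborview). Both agree with about 3 months.

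**Convention.** SAP 7.2.1 gives 2 March 2020 as the last day on which both sites were enrolling, so Harborview's pause date is its first closed day. I assume the same for Cincinnati. Day 30 is enrolment date plus 30.

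**Who is affected.** Day 30 falls on or after the pause if enrolment falls on or after pause minus 30 days.

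| | Cincinnati | Harborview |
|---|---|---|
| IF evaluation start | 8 Apr 2019 | 2 Jul 2019 |
| Pause | 13 Mar 2020 | 3 Mar 2020 |
| Pre-pause IF days | 340 | 245 |
| Affected enrolment dates | 12 Feb to 12 Mar 2020 | 2 Feb to 2 Mar 2020 |
| Their Day-30 dates | 13 Mar to 11 Apr 2020 | 3 Mar to 1 Apr 2020 |
| Share of pre-pause IF days | 30/340 = 8.8% | 30/245 = 12.2% |
| Day 44 for the last enrollee | 25 Apr 2020 | 15 Apr 2020 |

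The other two sites are clear: their last IF enrolment dates, 8 October 2019 and 5 January 2020, give last Day-30 dates of 7 November 2019 and 4 February 2020.

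**Expected numbers**, at the planned 10 per site per month (SAP 4.1.1) and 30.44 days per month:

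- Affected: 60/30.44 × 10 = 19.7, about 20.
- Two paused sites, pre-pause IF: (340 + 245)/30.44 × 10 = 192. Share: 60/585 = 10.3%.
- All four sites, pre-pause IF: 192 + 2 × 12 × 10 = 432. Share: 19.7/432 = 4.6%.

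At 12 per month (the upper planned rate in protocol 6.2) the affected number is about 24 and the shares are unchanged.

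**Effect on the IF engagement rate.** The shift is the affected share times the change in engagement among those affected. The documents give no such change, so these are assumptions:

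- A change of 10 to 20 points: overall 4.6% × 10 to 20 = 0.5 to 0.9 points; at the two sites 10.3% × 10 to 20 = 1.0 to 2.1 points.
- Extreme case, all affected participants scored not engaged, against the planned 40-50% (protocol 12.5): overall 1.8 to 2.3 points; at the two sites 4.1 to 5.1 points.

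**Does another provision cover this?** The second COVID-19 analysis only removes the pause from the time scale of later enrollees. The 44-day analysis in SAP 7.5.4 restricts the timing of the self-report relative to enrolment, not its calendar date. The model's time term in SAP 7.4 is enrolment time, and the Revised SAP section drops time without amending 7.5.2.

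**The case against.** The strongest reply is that this matters little. It is a supportive analysis of an outcome that SAP 9.0 treats as secondary, and no primary p-value or power figure rests on it. With 480 baseline and 432 pre-pause IF participants, 25% against an assumed 45% engagement, and clustering ignored, the standard error of the difference is √(0.25 × 0.75/480 + 0.45 × 0.55/432) = 3.1 points. A shift of 0.5 to 0.9 points is 0.15 to 0.3 of that, against a planned effect of 15 to 25 points. A changed conclusion is unlikely. This stands, and it limits the weight of the point.

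Second, section 7.5.2 could be read as a data cut at closure rather than a selection by enrolment date. That does not rescue the rule. The same participants would then have no Day-30 outcome and, unless excluded, would be counted as not engaged under SAP 7.5.3, which is the extreme case above.

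Third, the patient report may be taken by telephone (SAP 7.5.3), which limits lost contact. This stands in part: it does not alter the Day-30 date or the need for facility confirmation.

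A reader might also infer that the analysis is biased in a known direction, or that the pandemic explains the one site where the Revised SAP section reports lower engagement in the IF evaluation period (interaction p = 0.021). The documents support neither. They give no engagement figures for the affected month and do not name that site.

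**Conclusion.** The rule is wrong as written for the primary effectiveness outcome and sound for the primary implementation outcome. By the SAP's own dates, about one month of enrollees at each of two sites is labelled pre-COVID while carrying an outcome dated on or after the pause. The claim of no coronavirus effect therefore does not hold for engagement.

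The size is modest: about 20 participants, 10.3% of the two sites' and 4.6% of all sites' pre-pause IF enrolment. These counts rest on the planned rate and even accrual; actual monthly counts are not given. The site pause date stands in for the start of pandemic influence because it is the marker that the SAP uses. Bias is possible, not shown. The point does not reach the main analyses, nor other Day-30 outcomes, for which 7.5.2 plans no such analysis.

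**What to change.** In SAP 7.5.2, for the primary effectiveness outcome only, define the pre-COVID set as participants whose Study Day 30 falls before their site's pause date. The last eligible enrolment dates are then:

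- University of Cincinnati: 11 February 2020, inclusive (310 of 340 pre-pause IF days kept).
- Harborview: 1 February 2020, inclusive (215 of 245 kept).

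Keep the pause-date cut for the implementation outcome. Replace the wording about a true effect free of coronavirus with a qualified statement: outcomes are dated before the site's pause, but follow-up contact and facility confirmation, which can run to day 44 or later, may still fall after it. If Table 29 has already been produced, rerun the pre-COVID row for engagement or footnote it.

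The cost is one sentence, one date condition in the code, and about 20 fewer participants (about 24 at 12 per month) in a single sensitivity analysis, with a slight loss of precision.

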7.2 Analysis of the Primary Implementation Outcome Measure

For the primary implementation outcome measure, a Generalized Linear Mixed Model will be used to compare the rates of provision of ED-initiated BUP with referral for ongoing MAT between the baseline and IF evaluation periods. The model for the primary analysis will be used to compare the rates of ED-initiated BUP with referral for ongoing MAT between the IFEP and the BEP is:

$$\text{logit}(p_{si}) = \alpha + \beta t_{si} + \gamma f_{si} + r_s$$

where

- p_{si} is the probability of success of patient participant i at site s ,
- t_{si} is the calendar time of enrollment of patient participant i at site s ,
- f_{si} is the indicator of whether patient participant i at site s is in the BEP ($f_{si}=0$) or IFEP ($f_{si}=1$), and
- r_s is the random effect of site s , where $r_s \sim N(0, \sigma^2)$.

In this model the γ estimate represents the estimated difference in the logit of the probability of success and captures the effect of implementation facilitation. Note that calendar time is measured in days and defined in Section 3.3.6. The model will test a one-tailed hypothesis at the 0.05 level. The null and alternative hypotheses are:

$$H_0: \gamma \leq 0$$

$$H_a: \gamma > 0.$$

The following SAS code fragment estimates this model:

```
proc glimmix data = primout method = quad;
  class arm (ref="1") site;
  model z = arm time / dist = binomial link = logit solution;
  random intercept / subject = site;
  estimate "trt effect" arm 1 -1 / cl;
  lsmeans arm / cl ilink;
run;
```

where

- primout is the dataset containing the variables required for the primary outcome analyses;
- arm is 1 for the BEP and 2 for the IFEP;
- z is an indicator of the ED-initiated BUP (primary implementation outcome measure); and

- time is defined in Section 3.3.6.

The main focus for estimation is the estimated Risk Difference (RD) defined as the difference between IFEP and BEP success rates, ($p_{IFEP} - p_{EP}$) with its 95% credible interval (CI). The estimated RD and its 95% CI will be obtained using the Bayesian approach outlined in the protocol Appendix 19.0 and in this SAP. Below is the SAS code used for analyzing the primary implementation outcome for this model:

```
proc mcmc data = simmsimul nbi = 1000 nmc = 10000 thin = 2 seed = 159  
monitor =(alpha-gammacoeff gammacoeff_gt_0 p1 p2 pdiff) statistics = (summary  
intervals);  
  parms alpha-gammacoeff 0;  
  parms sigma2 1;  

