Evaluation of the distributional properties of the time variable data indicated that this variable, originally included as one of the explanatory factors in the analytical model, overlaps 96% with the intervention/treatment factor in the study. Including two highly overlapping variables in the analytical model can create a computational, statistical, and mathematical error. Collinearity, or high association between two explanatory variables means that the collinear variables contain the same information about the dependent variable, and that these only nominally different measures actually quantify the same

phenomenon or information. In CTN-0069, the variables “time” and “arm” are highly redundant. The best and most statistically robust analytical models are called “low noise” models in which the predictor variables each correlate highly with the outcome variable but correlate with each other at most only minimally. Collinearity and redundancy may lead to a failure to reject a false null hypothesis of no intervention effect. Consequently, the “time” variable was removed from the adjusted computational model.

Site. Additionally, the four geographically diverse study sites were purposefully selected to represent different clinical contexts and different patient populations. Conceptually, these EDs cannot be considered as a random sample of all EDs in the US, and probabilistically, no four values selected from a large population can be considered to represent randomness, even if they are drawn by chance. Consequently, site was included in the primary analytic models as a fixed effect, and not a random one in order to provide additional information on between site differences. The study results demonstrated not only statistical difference effects between the sites, but also substantial, large, important, and informative site differences.

Thus, the final analytic model for both the primary implementation and effectiveness outcomes was a logistic regression model with fixed effects for site and evaluation period.

Site Differences for Primary Effectiveness Outcome

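### With time dropped from the final model, the pause-removed COVID sensitivity analysis cannot test the reported primary result, and the SAP was not updated to say so

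*SAP*

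**What the plan says.** SAP 7.5.2 sets two COVID-19 sensitivity analyses for both primary outcomes. In the first, the closing date at the paused sites is treated as the end of the study, and "the analysis will be performed using only pre-COVID-19 data". In the second, "the data entered after sites reopened their ED will be converted so that the pause in enrollment is removed". The stated purpose of the second is narrow: "This will show whether the 3-month delay in recruitment due to COVID-19 had an impact" on the two primary analyses.

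Both were designed around the model of SAP 7.2 and 7.4, which has linear time: "model z = arm time / dist = binomial link = logit solution", plus a random site intercept. SAP 3.3.6 defines the variable: "Calendar time for analysis is defined as the number of days since the site opened for enrollment in the baseline evaluation period". It also records that "enrollment was paused due to the COVID-19 public health measures put into place at two sites", and that the paused days count in the primary analysis.

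The Revised SAP (Analytic Model Adjustments, at the end of the SAP) then changes the model. The time "variable was removed from the adjusted computational model", and the final model for both primary outcomes is a logistic regression with fixed effects for site and evaluation period. That section does not mention the COVID-19 analyses. The shells of Tables 21 and 29 still carry a row "COVID pause removed", with a GLMM coefficient and p-value and a Bayesian risk difference at two time points.

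**The concern.** The second analysis alters one thing only, the enrolment time of patients recruited after reopening. Once time has left the model, that alteration has nothing to act on. A planned check on the pandemic delay has been disabled by a later modelling decision, and no document says so.

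The risk lies in how the row is read. A result identical to the primary one would look like robustness to the delay, when no other result was possible. If the row was instead produced with the earlier mixed model, it would sit beside a primary result from a different model and could be taken to support it.

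**Working it through.** **1. The plan's own figure.** From the SAP 3.3.6 table, Cincinnati was paused from 13 March to 10 June 2020 (89 days) and Harborview from 3 March to 6 June 2020 (95 days). At 30.4 days per month these are 2.9 and 3.1 months, which agrees with the 3-month delay in 7.5.2.

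**2. What the analysis changes.** For post-reopening patients, t becomes t − 89 or t − 95. Outcome, site, period and the set of patients stay the same.

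**3. What the final model uses.** With y successes among n patients in site s and period f (0 or 1), the model is logit(p) = a_s + γf. Its log-likelihood is the sum over s and f of

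y_sf (a_s + γf) − n_sf log(1 + exp(a_s + γf)).

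No term contains t, and y_sf and n_sf are unchanged by step 2. The estimate, standard error and p-value are therefore identical. The risk difference is too, apart from Monte Carlo noise if an MCMC run uses another seed. The risk differences at the two time points in the shells also collapse to one number.

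The ChangeToOne rule (SAP 7.2.1) does not break this. Whichever zero in an all-zero site-period is recoded, the count is the same. In a trial fit, recoding different zeros gave 1.5554 each time. With time in the model, the coefficient moved between 1.66 and 1.80.

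**4. Illustration.** Assumptions: 960 patients, 120 per site and period, spread evenly over the actual site calendars; rates of 0.05 and 0.25 from the protocol's low-baseline scenario; an invented post-reopening effect of +1.0 or −1.0 on the log-odds scale; site as a fixed effect throughout. Entries are the period log odds ratio.

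| Model | Analysis | Effect +1.0 | Effect −1.0 |
|---|---|---|---|
| Site + period | Primary | 1.969 | 1.769 |
| Site + period | Pause removed | 1.969 | 1.769 |
| Site + period | Pre-COVID only | 1.846 | 1.846 |
| Site + period + time | Time as recorded | 1.222 | 2.294 |
| Site + period + time | Pause removed | 1.373 | 2.173 |

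In the final model the pause-removed row never moves, whereas the pre-COVID row does respond. With time in the model, the row moves. But in 500 simulated data sets with no COVID effect at all, the shift from recoding time had SD 0.094 (range −0.34 to +0.25), so a difference there is not in itself a sign of impact.

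**5. How much data is involved.** Post-reopening enrolment days, counted inclusively, are 10 June to 6 July 2020 = 27 and 6 June to 4 October 2020 = 121, in total 148. Active IF days at the two sites are (340 + 27) + (245 + 121) = 733, and 148/733 = 20.2%.

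Patient numbers need an accrual assumption: 148/30.4 = 4.87 months, so about 49 patients at 10 per month (the SAP 4.1.1 rate), 58 at 12, and 24 at an assumed 5. Against 480 planned IF patients, 49 is about 10%. An assumed 20-point change in their outcome would move the pooled IF rate by 49/480 × 20 = 2.0 points (1.0 with 24 patients, 2.4 with 58). The pause-removed row in the final model would show a change of 0.

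**The case against.** The strongest reply is that the documents never say this row was run in the final model. The Revised SAP refers in general to the model used in the planned analyses, which favours that reading. However, its closing sentence names only the two primary outcomes, and the shells keep the time-based layout. In the mixed model the row is not empty, as the table shows. This stands: the identity is conditional on the final model. It does not rescue the row, because a check run in an abandoned model says nothing direct about the reported result.

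A reader might go further and infer that the trial gives false reassurance about the pandemic as a whole. The documents do not support that. SAP 7.5.2 gives the pandemic question to the pre-COVID cut and only the delay to the second analysis. The pre-COVID cut drops patients, so it still works in the final model. Nor is any COVID-19 sensitivity result reported: the shells hold placeholders, so misreading is a risk and not a documented event.

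It can also be said that a model without time cannot be distorted by a calendar gap, so a zero change is redundant and not misleading. That is fair if the row is labelled so, and at present it is not. Finally, the patient count is assumed. SAP 11.0 reports very uneven baseline recruitment, so 49 is only indicative.

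**Conclusion.** The point holds in a limited form. In the final site-and-period model the pause-removed analysis equals the primary analysis by construction, for both outcomes. In the original time-adjusted model it examines something no longer primary. On neither reading can it show whether the delay affected the reported primary result, and the SAP does not say which reading applies.

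The exact identity rests only on the two model statements in the SAP. The size (20% of active IF days at two sites, perhaps 24 to 58 patients, and about 2 points on the pooled IF rate for an assumed 20-point change) rests on accrual and effect assumptions and is modest. This is worth correcting, but it does not undermine the primary analysis, and the pre-COVID-only check remains available.

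**What to change.** 1. State which model was used for each row of Tables 21 and 29.
2. Mark the pause-removed row not applicable under the final model, or label it as belonging to the original time-adjusted model and show that model's main result beside it.
3. Keep the pre-COVID-only analysis, fitted in the final model, as the main COVID-19 check.
4. In place of the empty row, fit the site-adjusted model with a three-level period (baseline, IF before pause, IF after reopening). Report after-versus-before with an interval for both outcomes.
5. For engagement, also classify patients by Day-30 date. Those enrolled in the last 30 days before the pause reach Day 30 during it (about 20 patients over the two sites at 10 per month).

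The cost is some SAP wording and recoded period variables; no new data are needed. The drawback is that the after-versus-before contrast comes from two sites, one with only 27 post-reopening days (about 9 patients at 10 per month). It will be imprecise. It is also confounded with longer exposure to facilitation, which continues through the IF evaluation period (Protocol 11.2). It should be presented as descriptive.
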